Six-Minute Walk Test		X	X	X
Short Physical Performance Battery		X	X	X
QoL Questionnaires		X	X	X
Health Literacy Questionnaire		X		
Echocardiogram		X		X
^{99m} Tc-PYP Scintigraphy**		X		
Phone Call Follow-Up [¶]			X	X

* Follow-up visits are to be conducted on subjects who test positive to the Cardiac Amyloid Scintigraphy scan and/or are carrier of the V122I mutation. Window for the 6-month visit is ±2 weeks and for the 12-month visit is ±4 weeks.

† Height measured only at baseline visit. Subjects with weight >350 lb will not participate in the study.

‡ Includes BNP, NT-proBNP, galectin-3, troponin I and T.

§ Includes Vitamin A and RBP4 in on site spot urine.

¶ For participants with no TTR CA, a phone call follow-up will be conducted instead.

**In the event that PYP is unavailable due to supply shortage, the investigator has the option of using HDP until PYP becomes available again to ensure study continuation per FDA.

For every study visit, a checklist will be used to help ensure completion of all the study procedures. The checklist is also a guide that suggests the order in which the assessments should be performed (See [Appendix 3](#)).

TABLE OF CONTENTS

STUDY SYNOPSIS.....	2
LIST OF ABBREVIATIONS AND DEFINITIONS OF TERMS.....	9
1. INTRODUCTION	10
1.1 Background and Rationale	10
1.1.1 Transthyretin Biology	10
1.1.2 Transthyretin-mediated amyloidosis definition	10
1.1.3 Pathogenesis and Outcome.....	11
1.1.4 ATTR-CM and Heart Failure	11
1.2 ATTR-CM Population Burden.....	13
1.2.1 ATTR amyloid is an under-recognized cause of heart failure	13
1.2.2 Are Hispanics affected by TTR-CA?	14
1.2.3 TTR-CA from mutant protein has more severe phenotype than wild type	14
1.3 Natural History of Transthyretin Cardiac Amyloidosis	15
1.3.1 Clinical Characteristics and Outcome in ATTR-CA in TRACS	15
1.3.2 Predictors of Mortality	16
1.4 Therapeutic Options.....	17
1.4.1 Novel Therapies Require Early Identification of Affected Individuals	17
1.4.2 Tc-PYP & Tc-HMDP can detect TTR-CA without the need for an amyloid biopsy	
18	
1.4.3 Myocardial retention of Tc99-PYP is prognostic in TTR-CA	18

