2.1.5 Study Procedures

The timing of all procedures in this study is outlined in Table 4. Eligible patients will be identified. Patients who are interested in the study will have a screening visit to evaluate for eligibility and obtain informed consent. If patients qualify for study and do consent they will have their study visit within 4 weeks of screening. At that visit they will have all of the following testing done.

Table 4. Study Procedures

Procedure	Screening	Baseline	6 Months* (± 2 weeks)	12 Months* (± 4 weeks)
Informed Consent	X			
Inclusion and Exclusion Criteria	X			
Baseline History		X		
Height and weight [†]		X	X	X
Vitals Signs		X	X	X
Medications		X	X	X
Clinical Examination		X	X	X
Adverse Events Review		X	X	X
Electrocardiogram		X	X	X
Laboratory Analysis				
Basic Metabolic Panel		X	X	X
Hepatic Function Panel		X	X	X
Cardiac Biomarkers [‡]		X	X	X
Vitamin A/RBP4 in plasma/urine [§]		X	X	X

Prealbumin		X	X	X
TTR Kinetic Stability		X		X
TTR Gene Sequencing		X		
Ancestry Analysis		X		
Six-Minute Walk Test		X	X	X
Short Physical Performance Battery		X	X	X
QoL Questionnaires		X	X	X
Health Literacy Questionnaire		X		
Echocardiogram		X		X
^{99m} Tc-PYP Scintigraphy**		X		
Phone call follow-up [†]			X	X

* Follow-up visits are to be conducted on subjects who test positive to the cardiac amyloid nuclear scan and/or are carrier of the V122I mutation. Window for the 6-month visit is ± 2 weeks and for the 12-month visit is ± 4 weeks.

[†] Height measured only at baseline visit.

[‡] Includes BNP, NT-proBNP, galectin-3, troponin I and T.

[§] Includes Vitamin A and RBP4 in on site spot urine.

**In the event that PYP is unavailable due to supply shortage, the investigator has the option of using HDP until PYP becomes available again to ensure study continuation per FDA.

¶ For participants with no TTR CA, a phone call follow-up will be conducted instead.

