2.1.5.8 Phone Call Follow-Up

Participants who have no evidence of TTR CA and/or are not V122I mutation carriers will be followed-up by phone at 6 and 12 months to gather information about vital status and document reasons and dates of hospitalizations (if any occurred).

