2.1.7 Statistical Considerations and Sample Size

Power and Sample Size: The total enrollment proposed for this study is of 800 subjects: 600 Blacks and 200 Hispanics. Amongst them, we expect approximately 80-160 ATTR CA subjects and 640-720 non-amyloid controls. The sample size planned for each race/ethnicity group achieves 80% power to

detect, as in Aim 1: (1) a prevalence of ATTR-CA of 10-15%, (2) a two-fold difference in the prevalence of ATTRm between Blacks and Hispanics (i.e., 0.08 vs 0.04, respectively), as well as, a similar difference in the prevalence of ATTRwt between Blacks and Hispanics, (3) a difference as small as 0.03 (if one truly exists) in the prevalence of ATTRwt with respect to gender (male) distribution between the two race/ethnic groups, and (4) in the ATTR CA group alone, we plan to measure the hierarchical composite endpoint of death, heart failure hospitalization, and 30% decline in 6-minute hall walk after 1 year. A two-sided logrank test with an overall sample size of 80 subjects (40 in the ATTRwt and 40 in the ATTRm) achieves 82% power at a 0.05 significance level to detect a hazard ratio (HR) of 0.44 when the proportion of patients that did not progress in the mutant group is 0.60. This corresponds to a minimum difference of 15% in the probability of not having progressed past 12 months between the two groups.

Aim 2 focuses on comparing differences in TTR kinetic stability and RBP4 concentration between ATTR CA (N=80-120) and the non-amyloid group (N=680-720). These sample sizes generate >95% power to detect: Hypothesis 1) a minimum difference in RBP4 of 5, assuming SDs of 9 and 20 for ATTR CA and non-amyloid, respectively; Hypothesis 2) a mean change difference in TTR stability as small as 0.01, SD of 0.002.

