2.1.8 Data Analysis Plan

Descriptive statistics will be used to summarize subjects' demographics and study outcomes. Sample proportions with exact 95% confidence intervals will be used to estimate the overall prevalence of ATTRm CA in Blacks and Hispanics and by sex. All analyses will be performed in SAS v.9.4 (Cary,NC), at a significance level of 0.05.

AIM 1: Hypotheses 1-3: The differences in proportions for prevalence (#1), genetic mutation status (#2), and sex (#3) will be assessed using Chi-squared/Fisher Exact tests. The genetic ancestry analysis will use 500K SNP data to perform principal components analysis (PCA) and determine the percentage of African admixture in all participants. To identify the associations of rare genetic variants in the TTR gene in ATTR CA cases vs controls, we will utilize burden testing.⁹⁴ **Hypothesis 4:** The main analysis will use the Kaplan-Meier method to estimate the probabilities of the composite endpoint, with medians (95% CI) being reported for each group. Cox regression analysis will be performed to generate the hazard ratio (95% CI), and to allow adjustment for other covariates such as sex or race/ethnicity, or explore interaction with other variables including cardiac biomarkers, echo parameters, or QOL. Alternatively, we will apply and compare Finkelstein-Schoenfeld's unmatched approach⁹⁵ to the matched win ratio,⁹⁶ both methods being used for reporting composite endpoints, with more appropriate priority given to the more clinically important event, e.g. mortality. **Hypothesis 5:** We will test the clinic-based risk calculator that was previously developed and validated in a smaller matched cohort study.⁹⁷ The proposed 4-variable model included: RBP4, LVEF, inter-ventricular septal thickness, mean limb lead QRS voltage, and generated an ROC AUC >90%. This model will be tested in our larger cohort and assessed with respect to prediction capability (AUC ROC) and goodness-of fit (Hosmer-Lemeshow test). We also plan to fit additional multivariable logistic regressions using the variables collected employing variable selection/model-building strategies and comparing the

resulting model(s) to the one proposed above. The variables in the final clinical risk model will be based on weights from the multivariate model.

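### Aim 2 states power for a between-group change in TTR stability, but the design takes no second stability sample from non-carrier controls

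*Combined protocol and SAP*

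**What the plan says.** The Aim 2 paragraph of section 2.1.7 sets up a comparison "between ATTR CA (N=80-120) and the non-amyloid group (N=680-720") and continues: "These sample sizes generate >95% power to detect", listing as its Hypothesis 2 item "a mean change difference in TTR stability as small as 0.01, SD of 0.002". Section 2.1.8 sets analyses "at a significance level of 0.05".

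Table 4 in section 2.1.5, the matching synopsis schedule and the visit checklists in Appendix 4 place the TTR kinetic stability assay at baseline and month 12, and not at month 6. Who attends the follow-up visits is set by footnotes to the table. Footnote *: "Follow-up visits are to be conducted on subjects who test positive to the cardiac amyloid nuclear scan and/or are carrier of the V122I mutation". Footnote ¶: "For participants with no TTR CA, a phone call follow-up will be conducted instead". Section 2.1.5.8 says that those without evidence of TTR CA and/or without the mutation are "followed-up by phone at 6 and 12 months to gather information about vital status" and hospitalizations. The phone follow-up form in Appendix 4 has no entry for a sample.

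In section 2.1.6, Aim 2 Hypothesis 1 compares stability at baseline, and Hypothesis 2 concerns the association of stability with survival and progression. The Aim 2 analyses in section 2.1.8 are correlations and linear regressions, with no change-from-baseline term.

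**The concern.** A mean change needs two measurements per person. The power item takes its control count from the whole non-amyloid group, yet nearly all of that group has one stability measurement and then telephone contact. No analysis method can supply the missing 12-month values, so the stated power belongs to a contrast that the trial cannot estimate.

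Aim 2 is one of the study's two specific aims, and this is its only power statement for TTR stability. A 12-month assay will exist for some participants, so an analyst who took the item at its word could form a control group from whoever happened to be re-sampled. Among non-amyloid participants, those could only be mutation carriers. Section 1.1.4.3 presents tetramer destabilization as the prevailing explanation of how amyloidogenic TTR mutations act, so carriers cannot stand in for non-amyloid heart failure on this endpoint.

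**Working it through.** **1. Reproducing the stated power.** Inputs from 2.1.7: difference 0.01, SD 0.002 (taken as common to both groups), group sizes 80 v 720 and 120 v 680. Alpha is 0.05 from 2.1.8; sidedness is not given for Aim 2, so two-sided is assumed.

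SE = SD × √(1/n₁ + 1/n₂); power ≈ Φ(difference/SE − 1.96).

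- 80 v 720: SE = 0.002 × 0.1179 = 0.000236; 0.01/SE = 42.4; power about 100%.
- 120 v 680: SE = 0.002 × 0.0990 = 0.000198; 0.01/SE = 50.5; power about 100%.

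The claim of more than 95% is arithmetically correct for two groups of those sizes. The question is whether the groups have the data.

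**2. Who has the second measurement.**

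| Participant | 12-month contact | 12-month stability assay |
|---|---|---|
| Scan-positive (ATTR CA) | On-site visit | Yes |
| Scan-negative, non-carrier | Phone (footnote ¶, 2.1.5.8) | No |
| Scan-negative, Val122Ile carrier | Visit under footnote *; phone under footnote ¶; no visit in the synopsis design text, which follows those diagnosed with ATTR; unclear under the and/or in 2.1.5.8 | Only if footnote * governs |

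Non-carrier controls with a measurable change: 0.

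**3. How many scan-negative carriers there might be.** Section 1.2.1 gives 9 of 91 (10%) carriers among Black heart failure patients over 60 in an earlier trial. Section 2.1.7 plans ATTRm prevalences of 0.08 in 600 Blacks and 0.04 in 200 Hispanics. Assume carrier rates of 8-10% in Blacks and 4-5% in Hispanics; the documents give no Hispanic rate.

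- Expected ATTRm CA: 600 × 0.08 + 200 × 0.04 = 56.
- Carriers, low: 600 × 0.08 + 200 × 0.04 = 56, leaving 0 scan-negative.
- Carriers, high: 600 × 0.10 + 200 × 0.05 = 70, leaving 14 scan-negative.
- 14/720 = 1.9% and 14/680 = 2.1% of the stated control group.

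The 10% is imprecise: the exact 95% interval for 9/91 is 4.6% to 17.9%. For Blacks alone, the lower limit gives (0.046 − 0.08) × 600, which is below zero. The upper limit gives (0.179 − 0.08) × 600 ≈ 60, or 8-9% of 680-720. At any point in this range, every re-sampled control is a carrier.

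**4. Power for comparisons the design does support, at the same 0.01 and 0.002.**

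- Baseline, ATTR CA v non-amyloid: as in step 1, about 100%.
- 12-month change, ATTRm v ATTRwt, 40 v 40 (the split used for Aim 1 in 2.1.7): SE = 0.002 × √(2/40) = 0.000447; 0.01/SE = 22.4; power about 100%.

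The documents do not say whether 0.002 is the SD of a change or of a single measurement. The largest SD that keeps 95% power for 0.01 is 0.01/(3.605 × √(1/n₁ + 1/n₂)): 0.0235 for 80 v 720, 0.0280 for 120 v 680 and 0.0124 for 40 v 40. There is ample room in each case.

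**The case against.** The strongest reply is that one loose word is being treated as a planned analysis. The same paragraph introduces Aim 2 as comparing differences in stability and RBP4 between the groups, Hypothesis 1 is a baseline comparison, and section 2.1.8 contains no change model. All of that can be done on baseline samples. This reading is plausible. It does not rescue the item, which carries the Hypothesis 2 label although that hypothesis is about outcomes, and which describes a quantity found in neither the hypotheses nor the analysis plan. Under either reading, the text needs the same correction.

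Four stronger conclusions that a reader might draw are not supported:

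- *No control has a second sample.* Footnote * would bring scan-negative carriers back on site. The statement holds for non-carriers.
- *The study is underpowered for stability.* At a difference of five SDs, power is nearly insensitive to group size; even 80 v 2 gives more than 99%. The defect is missing and unrepresentative control data.
- *The contrast would be biased in a known direction, say toward no difference.* The documents do not fix a direction. Section 2.2 leaves patients free to receive approved therapy, and section 1.4.5 reports that tafamidis stabilizes TTR, so treated cases could change more than carriers do.
- *The gap also undermines change in RBP4, biomarkers, walk distance or echo against controls.* No such case-control analysis of change is planned or powered; the progression endpoint is set within ATTR CA alone.

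**Conclusion.** The point stands as an internal inconsistency that should be corrected. As written, the Hypothesis 2 power item in 2.1.7 describes a comparison that the sampling schedule cannot deliver for the 680-720 controls on which it relies. Usable controls for change number zero among non-carriers. Scan-negative carriers might add about 0-14 under the planning rates, or up to about 60 at the upper limit of the carrier rate, and would be the wrong comparison group. The counts rest on an assumed Hispanic carrier rate, on the planned ATTRm prevalences, and on a carrier rate from a trial population with lower ejection fractions than this study enrols. The conclusion does not depend on the exact count. Neither the power arithmetic nor the sample size is in question; what must change is the comparison that the trial may claim to be powered for.

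**What to change.** In section 2.1.7, restate the TTR stability item as the baseline (cross-sectional) mean difference between ATTR CA and non-amyloid heart failure, say which SD the 0.002 is, and withdraw the power claim for between-group change. In 2.1.7 and 2.1.8, state that any analysis of 12-month change in TTR stability is limited to ATTR CA, ATTRm versus ATTRwt, with power given for those group sizes. State also that scan-negative carriers are not pooled as non-amyloid controls for change. Reconcile footnotes * and ¶ of Table 4 and of the synopsis schedule, the synopsis design text and section 2.1.5.8 on how scan-negative carriers are followed; which rule applies is for the sponsor to settle.

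The cost is wording only. No visits, samples or participants are added, and the restated comparisons keep about 100% power at the stated difference and SD. What is given up is the claim to a powered longitudinal contrast with controls.

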2.1.8 Data Analysis Plan

Descriptive statistics will be used to summarize subjects' demographics and study outcomes. Sample proportions with exact 95% confidence intervals will be used to estimate the overall prevalence of ATTRm CA in Blacks and Hispanics and by sex. All analyses will be performed in SAS v.9.4 (Cary,NC), at a significance level of 0.05.

AIM 1: Hypotheses 1-3: The differences in proportions for prevalence (#1), genetic mutation status (#2), and sex (#3) will be assessed using Chi-squared/Fisher Exact tests. The genetic ancestry analysis will use 500K SNP data to perform principal components analysis (PCA) and determine the percentage of African admixture in all participants. To identify the associations of rare genetic variants in the TTR gene in ATTR CA cases vs controls, we will utilize burden testing.⁹⁴ **Hypothesis 4:** The main analysis will use the Kaplan-Meier method to estimate the probabilities of the composite endpoint, with medians (95% CI) being reported for each group. Cox regression analysis will be performed to generate the hazard ratio (95% CI), and to allow adjustment for other covariates such as sex or race/ethnicity, or explore interaction with other variables including cardiac biomarkers, echo parameters, or QOL. Alternatively, we will apply and compare Finkelstein-Schoenfeld's unmatched approach⁹⁵ to the matched win ratio,⁹⁶ both methods being used for reporting composite endpoints, with more appropriate priority given to the more clinically important event, e.g. mortality. **Hypothesis 5:** We will test the clinic-based risk calculator that was previously developed and validated in a smaller matched cohort study.⁹⁷ The proposed 4-variable model included: RBP4, LVEF, inter-ventricular septal thickness, mean limb lead QRS voltage, and generated an ROC AUC >90%. This model will be tested in our larger cohort and assessed with respect to prediction capability (AUC ROC) and goodness-of fit (Hosmer-Lemeshow test). We also plan to fit additional multivariable logistic regressions using the variables collected employing variable selection/model-building strategies and comparing the

resulting model(s) to the one proposed above. The variables in the final clinical risk model will be based on weights from the multivariate model.

AIM 2: Hypothesis 1 and 3: Means (95% CI) and/or medians (inter-quartile range) will be computed for all continuous measurements including RBP4/TTR concentrations. Pearson/Spearman correlation coefficients will be calculated to quantify the strength of the association between RBP4 plasma and urine concentrations in the overall ATTR CA cohort and separately by ATTRm vs. ATTRwt groups. Linear regression models will be used to assess differences in TTR kinetic stability between the two groups, adjusting for RBP4 concentration and vitamin A. **Hypothesis 2:** In addition to descriptive statistics, linear regression models will be employed to test the associations between RBP4 concentration, TTR stability, and cardiac amyloid scintigraphy heart to contralateral chest ratio between the two groups, ATTR CA vs non-amyloid HF controls, adjusting for clinical characteristics and retinol concentration.

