2.1.3 Patient Recruitment

The SCAN- MP study is designed to identify a sufficient number of cases to support the following analytical objectives:

1. Stratify prevalence of ATTR-CA in subjects with HF by relevant demographic characteristics (gender, race/ethnicity, genotype); and
2. Evaluate relationships among ATTR-CA and baseline risk factors (presence of Val122Ile mutation and others) with disease outcomes.

To accomplish these objectives, a hybrid approach to cohort identification and selection is used that combines deliberate selection of subjects with heart failure who are at increased risk for ATTR-CA and selection of participants with relevant characteristics (age, gender, race/ethnicity, country of origin). Planned proportion of enrolled subjects by relevant characteristics is shown in the Table 3. Community involvement is essential for its success and recruitment will involve intensive community engagement through various means among the sites. In aggregate, we will recruit an equal number of men and women from the racial/ethnic groups. The expected marginal distributions of race/ethnicity are shown in Table 3. We will have overlapping ethnic groups among centers to minimize confounding of ethnicity by site. As recruitment of elderly members of minority groups is challenging, toward end of the recruitment period, participants will be asked to refer elderly persons to the study.

Table 3. Planned Enrollment by Age, Race, and Gender

Age (yr)	Black		Hispanic or Latino ethnicity		Total	
	M	F	M	F	M	F
≤75	150	150	50	50	200	200
>75	150	150	50	50	200	200

At CUMC we have seen 24,682 unique patients with HF over the last five years of which 2,969 (12%) self-identified as Black and 4,387 of 14,466 (29.9%) patients who declared their ethnicity were Hispanic and whose average age was 63 years. Harlem Hospital provides health care services to the primary service area of Harlem, Washington Heights/Inwood and the South Bronx with the vast

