2.1.5.4 Laboratory Analysis

Blood will be drawn and analyzed for standard chemistry (Chem-7), liver function, BNP, NT-proBNP, galectin-3, troponin I and T, vitamin A, retinol binding protein 4 (RBP4) and prealbumin. BNP, TnT, Gla-3, TnI and NT-proBNP will be measured through a research agreement with Abbott Laboratories, while the others are measured by local or affiliated research laboratories. Additionally, the kinetic stability of plasma TTR will be assessed at Scripps Laboratories using the published subunit exchange strategy, in which recombinant tagged TTR homotetramers are added to human TTR in plasma at equal concentrations to measure the rate at which the subunits exchange⁸⁰. Tetramer dissociation is the rate-limiting step for subunit exchange and for amyloidogenesis. We hypothesize that those individuals at risk for developing WT ATTR-CA produce WT TTR exhibiting inferior kinetic stability. Quantification of TTR kinetic stabilization could serve as a surrogate biomarker for the prediction of clinical outcomes and could become part of a risk calculation or an early diagnosis strategy, after validation. Additional aliquots will be used for genetic analysis (see below) and stored at -80° for analysis in the future. Ancestry analysis will also be performed on all participants. Urine specimen will be analyzed for Vitamin A and RBP4 measurements, to learn whether its levels differ among subjects with TTR amyloidosis, and to learn more about the specific physiology of the disorder.

TTR Gene Sequencing: Genotyping will be performed on genomic DNA obtained from blood from participants for the Val122Ile mutation using a PCR-based assay in the CLIA certified laboratory at Boston University.

Ancestry Analysis: Ancestry information will be obtained after buffy coat samples are extracted from participants' blood. Analysis for ancestry will take place in a specialized laboratory at Columbia University.

CCRLE and NIH Repository: Several specimens collected during the study will be stored indefinitely in a -80°C freezer located at the CCRLE lab and used for future analysis. Some of these samples will ultimately be transferred to a NIH repository.

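### Section 2.1.3 names confounding of ethnicity by site, but the Black v Hispanic tests in 2.1.8 ignore site; if both ethnic mix and prevalence differ between sites, a spurious ethnic difference can result.

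*Combined protocol and SAP*

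**What the plan says.** Section 2.1.3 (Patient Recruitment) states the threat and its answer together: "We will have overlapping ethnic groups among centers to minimize confounding of ethnicity by site". For Boston it adds an intention to recruit as many participants as the CUMC site, with a similar demographic distribution. Table 3 plans equal numbers of men and women, and of participants up to and over 75 years, within each ethnic group. Neither the text nor Table 3 gives Black or Hispanic numbers for any site.

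Section 2.1.8 (Data Analysis Plan) says that the differences for Aim 1 Hypotheses 1-3 "will be assessed using Chi-squared/Fisher Exact tests", "at a significance level of 0.05". It names no stratum or covariate for them. Exact confidence intervals are planned for ATTRm prevalence by ethnic group and by sex; these are descriptive. In Aim 1, covariate adjustment of a group comparison appears only in the Hypothesis 4 Cox model, "to allow adjustment for other covariates such as sex or race/ethnicity"; site is not among the examples. No analysis in the documents names site.

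Section 2.1.7 gives the sizes: "The total enrollment proposed for this study is of 800 subjects: 600 Blacks and 200 Hispanics". It says "The sample size planned for each race/ethnicity group achieves 80% power" for, among other things, a two-fold difference in ATTRm prevalence ("i.e., 0.08 vs 0.04, respectively").

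**The concern.** Overlap of the ethnic groups across centres makes a within-site comparison possible. A pooled two-by-two test does not make that comparison. It compares all Black with all Hispanic participants, so any difference between sites in case mix or in how cases are found enters the ethnic contrast in proportion to the imbalance in enrolment.

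Hypothesis 2 is itself a comparison of ethnic groups, so the interpretation of that result is at stake. The protocol recognised the risk at recruitment but did not carry it into the analysis. An adjustment chosen after the data are seen would be less convincing than one written down beforehand.

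**Working it through.** **1. The plan's own power figure.** Inputs from 2.1.7: 600 Black, 200 Hispanic, ATTRm prevalence 0.08 v 0.04. Alpha is 0.05, taken as two-sided because 2.1.8 does not state sidedness.

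- Pooled prevalence = (48 + 8)/800 = 0.07.
- Null SE = √[0.07 × 0.93 × (1/600 + 1/200)] = 0.02083.
- Alternative SE = √[0.08 × 0.92/600 + 0.04 × 0.96/200] = 0.01774.
- Power = Φ[(0.04 − 1.96 × 0.02083)/0.01774] = 48.1%.

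Exact enumeration gives 49.8% for chi-squared and 48.2% for Fisher. The most favourable variant tried (one-sided, unpooled) gives 72.9%. The stated 80% is not reproduced. The site point does not depend on this, but it means there is little power to spare.

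**2. Size of a spurious difference.** The documents give no prevalence and no enrolled mix by site, so both are assumed. Take two site groups, A and B, of 400 each, 600 Black and 200 Hispanic overall, and no ethnic difference within either group. The outcome is total ATTR-CA at 10% overall, the lower end of the 10-15% in 2.1.6.

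Worked case: A has 250 Black and 150 Hispanic (37.5% Hispanic), B has 350 and 50 (12.5%), and prevalence is 6% in A and 14% in B.

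- Black: (250 × 0.06 + 350 × 0.14)/600 = 64/600 = 10.7%.
- Hispanic: (150 × 0.06 + 50 × 0.14)/200 = 16/200 = 8.0%.
- Spurious difference: 2.7 points.
- SE used by the test = √[0.10 × 0.90 × (1/600 + 1/200)] = 0.0245.
- True SE of the crude difference = √[(250 × 0.06 × 0.94 + 350 × 0.14 × 0.86)/600² + (150 × 0.06 × 0.94 + 50 × 0.14 × 0.86)/200²] = 0.0228.
- Approximate rejection rate = Φ[(0.0267 − 1.96 × 0.0245)/0.0228] + Φ[(−0.0267 − 1.96 × 0.0245)/0.0228] ≈ 17.5%.

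Simulation with 20,000 replicates gives 18.1% for this case. Simulated results for a range of assumptions:

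| Hispanic share, A v B | Site prevalence, A v B | Spurious difference (points) | Crude type I error | Site-stratified |
|---|---|---|---|---|
| 25% v 25% | 8% v 12% | 0 | 5.1% | 5.1% |
| 25% v 25% | 6% v 14% | 0 | 4.9% | 5.1% |
| 32.5% v 17.5% | 8% v 12% | 0.8 | 5.5% | 4.9% |
| 32.5% v 17.5% | 6% v 14% | 1.6 | 8.7% | 4.9% |
| 37.5% v 12.5% | 8% v 12% | 1.3 | 7.4% | 5.2% |
| 37.5% v 12.5% | 6% v 14% | 2.7 | 18.1% | 5.0% |
| 43.75% v 6.25% | 8% v 12% | 2.0 | 11.7% | 5.1% |
| 43.75% v 6.25% | 6% v 14% | 4.0 | 36.8% | 5.2% |

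With equal prevalence at both site groups (10% v 10%), the crude test holds its level whatever the mix (4.8-4.9%). Both conditions are needed.

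**3. Cost of stratifying.** For 0.08 v 0.04 with the same rates at both site groups, simulated power falls from 49.7% to 49.7% (no change) with equal mixes, from 50.1% to 47.2% with shares of 37.5% v 12.5%, and from 49.5% to 43.3% with 43.75% v 6.25%.

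**4. Sparseness.** Expected ATTRm cases are 600 × 0.08 = 48 Black and 200 × 0.04 = 8 Hispanic, spread over up to five sites.

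**The case against.** The strongest reply is that the design already deals with this. If Boston enrols the mix that 2.1.3 intends, and the other sites follow, the crude test has no site bias, as the equal-mix rows show. Ascertainment is also largely uniform: all participants are to be scanned and genotyped (2.1.2), each scan has three readers blinded to clinical information (2.1.5.2), and one CLIA laboratory does the genotyping (2.1.5.4). A crude prevalence comparison is a legitimate descriptive quantity. All this stands, and it makes the bias conditional. It does not remove it: the Boston mix is an intention for one site, and no ethnic numbers by site hold enrolment to it.

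Several stronger readings are tempting and are not supported:

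- **Catchment figures as proof of unequal enrolment.** A reader might compare the Black and Hispanic percentages that 2.1.3 gives for CUMC and Boston. The denominators differ: CUMC's 12% Black is of 24,682 heart failure patients, its 29.9% Hispanic is of the 14,466 who declared ethnicity, and Boston's figures are for all patients. Harlem's figures, which describe residents, would also have to be counted. Participants are moreover to be selected on race/ethnicity, so catchment mix need not equal enrolled mix.
- **Setting the spurious gap against the planned 4 points.** The 4-point difference is in ATTRm; the scenarios above concern total ATTR-CA.
- **Age and sex as equal threats.** Table 3 plans balance on sex and two age bands within each ethnic group. If it is met, mainly age within band remains.
- **Site confounding of the sex contrast.** Equal numbers of men and women are planned, and the documents give no mechanism for this.
- **Laboratory offsets throughout Aim 2.** Section 2.1.5.4 says of the assays not run under the Abbott agreement, "while the others are measured by local or affiliated research laboratories". That does not show that RBP4 is assayed separately by site. The Aim 2 models already adjust for some covariates (2.1.8, 2.2), and 2.1.8 specifies no model with vitamin A or prealbumin as outcome.

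**Conclusion.** The point holds in conditional form. The protocol names confounding of ethnicity by site, limits it only through recruitment, and plans tests of the ethnic contrasts that ignore site. Bias needs an unequal ethnic mix and unequal prevalence across sites together; the documents establish neither.

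With a moderately unequal mix (37.5% v 12.5% Hispanic), the crude type I error is about 7% to 18% over the assumed site prevalences. The milder imbalance gives about 6% to 9%. A site-stratified test stays near 5% throughout. These figures rest on assumed mixes and prevalences, two site groups and total ATTR-CA at 10%; the corresponding error rates for ATTRm or ATTRwt alone were not calculated. This should be changed in the analysis plan, but it does not invalidate the design.

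**What to change.** In 2.1.8, pre-specify for the Hypothesis 2 Black v Hispanic contrasts (ATTRm and ATTRwt) either a Cochran-Mantel-Haenszel analysis stratified by site, or a logistic model with site, age and sex. State in advance how small sites will be pooled, and that a Firth-penalised or exact method will be used if cells are sparse. Report the adjusted estimate with its 95% confidence interval beside the crude prevalences and the crude test. Age and sex are secondary terms, which protect the result if enrolment departs from Table 3.

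State in 2.1.5.4 whether RBP4 is assayed in one laboratory or several. A laboratory term is needed in the RBP4 analyses only if there is more than one.

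The cost is wording. Site number is part of each participant's identifier (2.3), and age and sex are on the demographics form (Appendix 4). The statistical price is a small loss of power, 43-50% stratified against 49-50% crude in the scenarios above, and sparse strata with about 8 Hispanic ATTRm cases expected.
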